8.3 ADVERSE EVENTS AND SERIOUS ADVERSE EVENTS

8.3.1 DEFINITION OF ADVERSE EVENTS (AE)

An adverse event is any untoward medical occurrence associated with the use of an intervention in humans, whether or not considered intervention-related (21 CFR 312.32 (a)). Further, an AE is any unfavorable and unintended or abnormal laboratory finding, symptom, or disease temporally associated with the use of a medical treatment or procedure, regardless of whether it is considered related to the medical treatment or procedure.

8.3.2 DEFINITION OF SERIOUS ADVERSE EVENTS (SAE)

An adverse event (AE) or suspected adverse reaction is considered "serious" if, in the view of either the investigator or sponsor, it results in any of the following outcomes: death, a life-threatening adverse event, inpatient hospitalization or prolongation of existing hospitalization, a persistent or significant incapacity or substantial disruption of the ability to conduct normal life functions, or a congenital anomaly/birth defect. Important medical events that may not result in death, be life-threatening, or require hospitalization may be considered serious when, based upon appropriate medical judgment, they may jeopardize the participant and may require medical or surgical intervention to prevent one of the outcomes listed in this definition. Examples of such medical events include allergic bronchospasm requiring intensive treatment in an emergency room or at home, blood dyscrasias or convulsions that do not result in inpatient hospitalization, or the development of drug dependency or drug abuse (21 CFR 312.32 (a)).

For this trial, adverse events meeting the definition of serious will be collected on all participants, regardless of their association with the study treatment, from the time of randomization to the end of a participant's follow-up.

8.3.3 CLASSIFICATION OF AN ADVERSE EVENT

8.3.3.1 SEVERITY OF EVENT

For adverse events (AEs) not included in the protocol defined grading system, the following guidelines will be used to describe severity.

- **Mild** – Events require minimal or no treatment and do not interfere with the participant's daily activities.
- **Moderate** – Events result in a low level of inconvenience or concern with the therapeutic measures. Moderate events may cause some interference with functioning.
- **Severe** – Events interrupt a participant's usual daily activity and may require systemic drug therapy or other treatment. Severe events are usually potentially life-threatening or incapacitating. Of note, the term "severe" does not necessarily equate to "serious".

8.3.3.2 RELATIONSHIP TO STUDY INTERVENTION

All adverse events (AEs) must have their relationship to study intervention assessed by the clinician who examines and evaluates the participant based on temporal relationship and his/her clinical judgment. The degree of certainty about causality will be graded using the categories below. In a clinical trial, the study product must always be suspect.

- **Related** – The AE is known to occur with the study intervention, there is a reasonable possibility that the study intervention caused the AE, or there is a temporal relationship between the study intervention and event. Reasonable possibility means that there is evidence to suggest a causal relationship between the study intervention and the AE.
- **Not Related** – There is not a reasonable possibility that the administration of the study intervention caused the event, there is no temporal relationship between the study intervention and event onset, or an alternate etiology has been established.

8.3.3.3 EXPECTEDNESS

The principal investigator will be responsible for determining whether an adverse event (AE) is expected or unexpected. As with our preliminary safety/tolerability study of fermented soy consumption in healthy volunteers (N=20) we would expect that mild, intermittent gastrointestinal (GI) symptoms (nausea, stomach pain, diarrhea, and/or distension) could occur in a minority of participants, and would more likely become known after the first few doses, at the beginning of the study. While subjects will be screened for known allergy to soy, there is a risk of allergic reaction. An AE will be considered unexpected if the nature, severity, or frequency of the event is not consistent with symptoms as described here.

8.3.4 TIME PERIOD AND FREQUENCY FOR EVENT ASSESSMENT AND FOLLOW-UP

The occurrence of an adverse event (AE) or serious adverse event (SAE) may come to the attention of study personnel during study visits and interviews of a study participant presenting for medical care, or upon review by a study monitor.

All AEs including local and systemic reactions not meeting the criteria for SAEs will be captured on the appropriate eCRF in OnCore®. Information to be collected includes event description, time of onset, clinician's assessment of severity, relationship to study product (assessed only by those with the training and authority to make a diagnosis), and time of resolution/stabilization of the event. All AEs occurring while on study must be documented appropriately regardless of relationship. All AEs will be followed to adequate resolution.

Any medical condition that is present at the time that the participant is screened will be considered as baseline and not reported as an AE. However, if the study participant's condition deteriorates at any time during the study, it will be recorded as an AE.

Changes in the severity of an AE will be documented to allow an assessment of the duration of the event at each level of severity to be performed. AEs characterized as intermittent require documentation of onset and duration of each episode.

The clinical trials manager will record all reportable events (AEs and SAEs) with start dates occurring any time after informed consent is obtained until the last day of study participation. At each study visit, the clinical trials manager will inquire about the occurrence of AE/SAEs since the last visit. Events will be followed for outcome information until resolution or stabilization.

8.3.5 ADVERSE EVENT REPORTING

An assessment of treatment relatedness is required for each event reported. The project's clinical team will generate tabulations of any AEs in the OnCore® system. A summary of all AEs believed to be related to the study intervention will be reviewed by the PI, who will then coordinate reporting of these events to the DSMC.

8.3.6 SERIOUS ADVERSE EVENT REPORTING

An assessment of treatment relatedness is required for each event reported. The project's clinical team will generate tabulations of SAEs in the OnCore® system. A summary of all SAEs believed to be related to the study intervention will be reviewed by the PI and co-investigators.

Unexpected SAEs that occur during the conduct of the trial will be expeditiously reported (within 24 hours of becoming known) by the Clinical Trials Manager to the study sponsor. The Sponsor-Investigator will report to the FDA (if deemed appropriate), as specified in the protocol.

Data on fatal or life-threatening SAEs will be reported by the Sponsor-Investigator, if required, to regulatory authorities as per 21 CFR 312.32(c)(2) as soon as possible but in no case later than 7 calendar days after initial receipt of the information (treatment assignment blinded) and will be tabulated and presented to the DSMC (treatment assignment blinded or unblinded as per DSMC decision).

In addition, the Sponsor-Investigator will notify FDA in an Investigational New Drug (IND) safety report of potential serious risks, from clinical trials or any other source, as soon as possible, but in no case later than 15 calendar days after the Sponsor-Investigator determines that the information qualifies for reporting.

8.3.7 REPORTING EVENTS TO PARTICIPANTS

Participants in this RCT will be informed should any SAEs develop during the course of the study, which would affect their willingness to participate. SAEs (and any significant new findings) will require urgent contact with current participants. Depending on the circumstances of the SAE, this may be extended to include informing previous and potential participants. Communications with each participant will be documented in their research record and in the Adverse Event eCRF in OnCore®. AEs will be evaluated individually as to whether they are product/study-related. If so, communications with each individual affected will be documented in the same manner.

Frequent opportunities will exist for an assessment of safety/tolerability, as participants will be called on a weekly basis throughout the intervention period of the study. Management (corrective action) of incidental findings will follow according to those outlined in Section 8.4.1, Definition of Unanticipated Problems (UP) and Section 8.4.2, Unanticipated Problem Reporting.

A description of this clinical trial and study-related results on an aggregate level will be will be available on the ClinicalTrials.gov clinical trial registry website.

8.4 UNANTICIPATED PROBLEMS

8.4.1 DEFINITION OF UNANTICIPATED PROBLEMS (UP)

The Office for Human Research Protections (OHRP) considers unanticipated problems involving risks to participants or others to include, in general, any incident, experience, or outcome that meets *all* of the following criteria:

- Unexpected in terms of nature, severity, or frequency given (a) the research procedures that are described in the protocol-related documents, such as the IRB-approved research protocol and

informed consent document; and (b) the characteristics of the participant population being studied;

- Related or possibly related to participation in the research (“possibly related” means there is a reasonable possibility that the incident, experience, or outcome may have been caused by the procedures involved in the research); and
- Suggests that the research places participants or others at a greater risk of harm (including physical, psychological, economic, or social harm) than was previously known or recognized.

This protocol presents minimal risks to the participants. Unanticipated Problems Involving Risks to Subjects or Others (UPIRSOs), including adverse events, are not anticipated. However, corrective actions or changes that may be considered in response to an Unanticipated Problem include:

- Modification of inclusion or exclusion criteria to mitigate the newly identified risks
- Implementation of additional safety monitoring procedures
- Suspension of enrollment of new participants or halting of study procedures for enrolled participants
- Modification of informed consent documents to include a description of newly recognized risks
- Provision of additional information about newly recognized risks to previously enrolled participants.

8.4.2 UNANTICIPATED PROBLEM REPORTING

Unanticipated Problems Involving Risks to Subjects or Others (UPIRSOs), including adverse events, are not anticipated in this study, as it presents minimal risks to participants. In the unlikely event that such events occur, “reportable events” (events that are serious or life-threatening and unanticipated) or events that are anticipated but may be occurring with a greater frequency than expected (whether they are possibly, probably, or definitely related), or any UPIRSOs that may require a temporary or permanent interruption of study activities, will be reported immediately (if possible), followed by a written report to the IRB, using the appropriate forms from the Yale Human Research Protection Program website as per their written policies and procedures. The appropriate funding and regulatory agencies will also be notified. The principal investigator will apprise fellow investigators and study personnel of all UPIRSOs and adverse events that occur during the conduct of this research project via email, as the PI would review them all.

The UP report will include the following information:

- Protocol title, IRB/Human Investigation Committee protocol number, and name of PI
- A detailed description of the event, incident, experience, or outcome
- An explanation of the basis for determining that the event, incident, experience, or outcome represents an unanticipated problem
- A description of any changes to the protocol or other corrective actions that have been taken or are proposed in response to the UP

To satisfy the requirement for prompt reporting, UPs will be reported using the following timeline:

- UPs that are serious adverse events (SAEs) will be reported to the IRB as per their written policies and procedures and to the study sponsor immediately (within 24 hours) upon the principal investigator becoming aware of the event.

- Any other UPs will be reported to the IRB as per their written policies and procedures and to the study sponsor within 5 calendar days of the investigator becoming aware of the problem.

The protocol's research monitor(s), e.g. Cancer Center Protocol Review Committee (PRC), Yale Cancer Center Data and Safety Monitoring Committee (DSMC) reviews entries of unanticipated problems in OnCore® at each meeting.

8.4.3 REPORTING UNANTICIPATED PROBLEMS TO PARTICIPANTS

The principal investigator or study personnel will inform participants about UPs which may affect them on an individual basis via preferred their means of contact, whether by phone, email or in person.

9 STATISTICAL CONSIDERATIONS

9.1 STATISTICAL HYPOTHESES

- Primary Efficacy Endpoint(s): Serum prostate-specific antigen (PSA)

The study is designed as a superiority trial; the primary comparison will be the main effects of QC vs. Placebo. This comparison will be made by assessing the change in serum PSA values (Time of admission for surgery – Baseline) of participants in the two study arms. A two-tailed p-value will be used with a Type I error of 0.05 as the level of statistical significance.

- Secondary Efficacy Endpoint(s):

Variables assessed pre and post-surgery are classified as secondary endpoints:

1. Volume of prostate gland
2. Volume of biopsy-proven, index prostate cancer lesion
3. Prostate cancer tissue telomeric DNA length
4. Cell cycle progression (CCP) score assessment of prostate cancer mRNA from prostate cancer tissue
5. Specific marker changes on PCa tissue microarrays (TMAs) using automated quantitative analysis (AQUA)
6. Gleason score compared to preoperative biopsies
7. Quality of life (FACT-P)
8. CAPRA-S (post-surgical CAPRA score)

9.2 SAMPLE SIZE DETERMINATION

The sample size calculation was based on the following assumptions:

PSA difference* = 15 units
Standard Deviation = 20.3
Power (Type II error) = 0.8
Type I error (two-sided) = 0.05

Repeated measures analysis design

Estimate of difference informed by results from Lazarevic et al.⁵

Interim Monitoring:

The use of the Peto method for the interim analysis (alpha level=0.001) would not necessitate any consideration for sample size adjustment.

9.3 POPULATIONS FOR ANALYSES

Intention-to-treat ('as randomized') analyses will be performed on all randomized participants. Duration of treatment will be taken into account in the analysis.

Per-protocol ('as-treated') analysis will also be carried out; assessment of treatment adherence will be based on self-reported reporting during phone follow-up calls.

The Safety Analysis dataset will include participants who took at least one dose of study medication.

9.4 STATISTICAL ANALYSES**9.4.1 GENERAL APPROACH**

Categorical data will be presented as counts and percentages. Continuous variables will be presented using mean with standard deviation and median with IQR. Graphical presentations will also be made as appropriate.

Two-tailed, Type I error of 0.05 and 95% Confidence intervals will be used in analyses.

The CAPRA score level (low/medium vs high) will be used to run a stratified primary outcome analysis. Other variables will be considered later in the SAP for use as covariates in subsequent analyses.

Normality of distributions of continuous variables will be assessed and transformations (e.g. log, square root) will be considered, as appropriate, to normalize not normal distributions. In the event that normality cannot be achieved, nonparametric tests will be employed.

9.4.2 ANALYSIS OF THE PRIMARY EFFICACY ENDPOINT(S)

The primary outcome is change in serum PSA. This is the difference between the PSA value at baseline and the value at the time of admission for surgery (prostatectomy).

'Baseline' is defined as the date that an eligible participant enrolls in the trial; randomization will occur within 3 days of baseline assessment. If no measurement is available in this 3-day window, the first measurement after randomization BUT before the date of treatment initiation and up to day 7, will be defined as baseline.

Repeated measures analysis or linear mixed models analysis will be used to assess whether the mean change in PSA from pre to post-treatment differs in the two groups. This can be achieved by measuring the (time by group) interaction term in a repeated measures ANOVA.

In secondary analysis of the primary outcome, the difference in PSA mean level at post-intervention/pre-surgery between the two groups will be assessed using ANCOVA and adjusting for pre-intervention/baseline values. This analytical approach will test whether the QC group has a higher PSA mean level following treatment. Adjusting for pre-treatment/baseline PSA level ensures that any post-treatment differences are a consequence of treatment, and not a result of some random effect from the pre-treatment differences between the groups. In addition, variation in the post-treatment means stemming from the variation introduced from the pre-treatment participant starting point.

Stratified analysis (low/medium vs. high CAPRA score) will also be carried out.

9.4.3 ANALYSIS OF THE SECONDARY ENDPOINT(S)

A number of secondary outcomes will be compared between the two trial arms.

A. Assessed pre and post-surgery

Continuous variables:

1. Volume of gland
2. Volume of biopsy-proven, index prostate cancer lesion
3. Prostate cancer tissue telomeric DNA length
4. Cell cycle progression score assessment of prostate cancer mRNA from prostate cancer tissue

Analysis will be carried out using linear mixed models to assess whether mean changes (pre to post-surgery) differs between the two groups.

Ordinal variables:

1. Gleason score compared to preoperative biopsies
2. Quality of life (FACT-P)

The Wilcoxon Signed Rank test will be used to analyze these variables.

B. Assessed post-surgery

Continuous variables

1. Automated quantitative (AQUA) immunofluorescence analysis of markers of prostate cancer aggressiveness on a tissue microarray
2. CAPRA-S¹¹ post-surgical score (a validated risk stratification tool incorporating PSA, pathologic Gleason score, surgical margin status, extracapsular extension, seminal vesicle extension, lymph node status (0-12 points)

Post-surgery comparisons of continuous secondary outcomes between the two study groups will be carried out using parametric (t-test) or non-parametric (Wilcoxon Rank Sum) as deemed appropriate (based on normality of distribution).

Categorical variables

1. Degree of tumor focality

Chi-square methods will be used to analyze this variable.

C. Assessed weekly for the duration of the study

1. Adverse events

The percentage and rate of adverse events will be compared between the two groups.

2. Adherence: Number of doses missed (assessed weekly from baseline to final visit)

Repeated measures/longitudinal analysis will be used to analyze adherence to QC.

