3 OBJECTIVES AND ENDPOINTS

OBJECTIVES	ENDPOINTS	JUSTIFICATION FOR ENDPOINTS
Primary		
To assess the efficacy of QC fermented soy vs. placebo in 72 adults with localized prostate cancer (PCa) prior to radical prostatectomy.	The primary assessment will be a comparison between participants in the QC arm vs. the placebo arm, in mean serum PSA (prostate-specific antigen) level changes, from baseline and time of admission for surgery.	Fermented soy supplementation/soy isoflavones are known to decrease serum PSA, the levels of which are used to indicate prostate health.

OBJECTIVES	ENDPOINTS	JUSTIFICATION FOR ENDPOINTS
Secondary	
To assess the efficacy of QC on disease progression (1, 2, 3, 4, 5), PCa biomarkers (6, 7), and quality of life (8).
 
1. Volume of prostate gland 2. Volume of biopsy-proven, index PCa lesion 3. Gleason score compared to preoperative biopsies 4. PCa tissue telomeric DNA length 5. Cancer of the Prostate Risk Assessment (CAPRA-S) score 6. Cell cycle progression score assessment of prostate cancer mRNA from PCa tissue 7. Specific marker changes on PCa tissue microarrays (TMAs) using AQUA - automated quantitative analysis 8. Functional Assessment of Cancer Therapy – Prostate (FACT-P v4[®])
	
1, 2, 3: Pathological investigation of the removed prostate gland, to analyze any modulation of PCa grade (Gleason score) compared to preoperative biopsies, volume of gland and of biopsy-proven, index prostate cancer lesion, and extent (involvement of surgical margins and extraprostatic extension) of clinical and pathological tumor stage and degree of tumor focality.
 
4. Analysis of telomere length in research samples of human peripheral blood mononuclear cells reveals that telomere length decreases with increased replication of cells, reflecting the replicative history of those cells.
 
5. Post surgical/post intervention CAPRA score for comparison with baseline
 
6. Cell cycle progression score assessment of PCa mRNA (from PCa tissue before and after treatment and between treatment arms) is a novel RNA expression-based assay that directly measures tumor cell growth characteristics in order to stratify patients with localized PCa according to disease aggressiveness.
 
7. AQUA can assess TMAs using fluorescent tags to define tumors, localize sub-cellular compartments, and grade intensity of specific markers on a continuous scale.
 
8. Quality of life assessment for men with PCa

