PHI (prostate health index, which gives total and % free PSA - prostate-specific antigen), ESR (erythrocyte sedimentation rate), CBC with Diff (complete blood count with differential), CMP (comprehensive metabolic panel), testosterone (total, bioavailable and free), CRP (C-reactive protein), lipase, lipid panel, amylase, TSH (thyroid stimulating hormone), estrogen, IGF-1 (insulin-like growth factor), IGFBP-1, IGFBP-2, and IGFBP-3 (insulin-like growth factor binding proteins).

- Nursing staff and phlebotomists at all sites are trained and certified in standard phlebotomy techniques.
- Total volume of blood to be drawn per subject visit is approximately 20-30 cc.

- A single, central processing laboratory (YNHH) will be used for all sites, to decrease variability in test results for the primary outcome, PSA.
- ***Special assays or procedures required*** – The following pathological analyses and assays will be performed after the study has closed to enrollment:
 - Pathological investigation of the removed prostate gland, analyzing any modulation of prostate cancer grade (Gleason score) and disease progression (CAPRA-S) compared to preoperative biopsies, volume of gland and of biopsy-proven, index prostate cancer lesion, and extent (involvement of surgical margins and extraprostatic extension) of clinical and pathological tumor stage and degree of tumor focality.
 - Telomere length (*TeloTAGGG™ Telomere Length Assay*) will be used to estimate telomeric DNA length from prostate cancer tissue.
 - Automated quantitative (AQUA) immunofluorescence analysis of markers of prostate cancer aggressiveness on a tissue microarray, using fluorescent tags to define tumors, localize sub-cellular compartments, and grade intensity of specific markers.

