- ***Instances when curative treatment plan changes*** – Should an enrolled participant's course of treatment change in that he would not undergo prostatectomy (such as undergoing radiation therapy instead), with the treating urologist's approval, the participant may elect to remain in the study, continue daily IP dosing and attend his final subject visit as scheduled. The primary outcome of the study is prostate-specific antigen (PSA), which can be obtained post-IP consumption regardless. It is accepted that the secondary outcomes (AQUA, CCP and telomere assay) comparing biopsied tissue with tissue from the resectioned prostate would be lost in these rare instances when individuals do not undergo surgical removal of their prostate.
- ***Administration of questionnaires, instruments and patient-reported outcomes*** - Participants will be asked to complete:
 - An inventory of soy-containing foods they have consumed within the past month at Screening/Baseline.
 - Pre/post FACT-P (Functional Assessment of Cancer Therapy - Prostate), a validated, 39-item questionnaire that measures health-related quality of life specific to men with prostate cancer, and assesses well-being in four domains (physical, social/family, emotional, and functional).
 - Participants will be given thorough dosing instructions for consuming the study drink, and will be asked to complete a daily dosing diary.

Follow-up procedures after administration: The final participant assessments will occur at Visit 2, approximately 24-48 hours prior to prostatectomy. No further follow-up by research personnel is planned at this time; patients will be followed by their treating urologist for clinical care.

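### AQUA and CAPRA-S are compared between arms with no baseline or stratum term, which gives up precision that the trial could have at little cost

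*Protocol*

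**What the plan says.** Protocol section 9.4.3 puts AQUA and CAPRA-S in its group of variables measured only after surgery and gives this rule: "Post-surgery comparisons of continuous secondary outcomes between the two study groups will be carried out using parametric (t-test) or non-parametric (Wilcoxon Rank Sum", as normality allows. In the same section, telomere length and the cell cycle progression (CCP) score get a linear mixed model for the change from before to after surgery.

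Other parts of the Protocol describe the two endpoints differently:

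- **AQUA.** Section 3 names the endpoint as "Specific marker changes on PCa tissue microarrays (TMAs) using AQUA - automated quantitative analysis". Section 8.1, on men who do not have a prostatectomy, refers to "secondary outcomes (AQUA, CCP and telomere assay) comparing biopsied tissue with tissue from the resectioned prostate".
- **CAPRA-S.** The justification column of section 3 reads "Post surgical/post intervention CAPRA score for comparison with baseline". Section 8.1 lists "disease progression (CAPRA-S) compared to preoperative biopsies" among the pathological analyses.
- **Both.** Section 9.1 introduces a list containing both with "Variables assessed pre and post-surgery are classified as secondary endpoints".

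On baseline data, section 6.3 stratifies randomization by CAPRA score (0–4 against 5–10). Section 10.1.9.1 says that biopsy reports are obtained to derive the score for that purpose. A footnote to the schedule in section 1.3 says that biopsy and excised tissue are both banked, and that consent covers the telomere, CCP and AQUA assays.

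On covariates, section 9.4.1 plans a CAPRA-stratified analysis for the primary outcome only. Section 9.4.5 considers adjustment for characteristics found to be unbalanced.

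The SAP, written after early termination, replaces full analysis of secondary outcomes with baseline, end-of-study and difference values (section 1). Its list of secondary outcomes (section 1.1.3) contains neither AQUA nor CAPRA-S.

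**The concern.** The analysis section does not match the sections that describe what the two endpoints are for. Three tissue assays are grouped together in section 8.1 as biopsy-against-resection comparisons. Two of them get a pre-to-post model, while AQUA gets a two-sample test on the resected tissue alone, and no reason is given. CAPRA-S is likewise compared without reference to the baseline risk score on which the randomization is stratified.

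Two things are at stake. The first is precision: in a small trial, a prognostic baseline left out of the model widens the interval. The second is a wrong calculation. Someone who reads sections 3, 8.1 and 9.1 literally, or applies the SAP's general rule of reporting a difference from baseline, could subtract a baseline CAPRA score from CAPRA-S, and that difference has no clear meaning.

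**Working it through.** **1. Is there a figure in the plan to reproduce?** Not for these endpoints: the documents give no effect size, SD, power or baseline correlation for AQUA or CAPRA-S. The only sample-size inputs, in section 9.2, are for PSA (difference 15, SD 20.3, power 0.8, two-sided 0.05). They give 2 × 2.802² × (20.3/15)² = 28.7, so 29 per arm or 58 in total by the normal approximation, against the 72 stated. That gap does not bear on this point. The planned 36 per arm is taken as given below.

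**2. Does any other provision supply the missing term?** No. The stratified analysis in section 9.4.1 is confined to the primary outcome. Section 9.4.5 depends on an imbalance being seen and names neither a biopsy AQUA value nor the CAPRA score. The ANCOVA in section 9.4.2 is for PSA.

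**3. What does omitting the baseline cost?** Let r be the correlation between the baseline covariate and the post-surgery outcome. In units of the outcome variance:

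- post-surgery value alone: 1
- ANCOVA on baseline: 1 − r²
- raw change score on a common scale with equal variances: 2(1 − r)

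The post-surgery test with 36 per arm, two-sided 0.05 and 80% power detects (1.960 + 0.842) × √(2/36) = 2.802 × 0.2357 = 0.66 SD. With ANCOVA this becomes 0.66 × √(1 − r²). Power at 0.66 SD is Φ(2.802/√(1 − r²) − 1.960).

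| Assumed r | ANCOVA variance factor | Equivalent sample-size factor, 1/(1 − r²) | Unadjusted N matching 72 with ANCOVA | Detectable difference (SD) | Power at 0.66 SD | Change-score variance factor |
|---|---|---|---|---|---|---|
| 0.3 | 0.91 | 1.10 | 79 | 0.63 | 83.6% | 1.40 |
| 0.5 | 0.75 | 1.33 | 96 | 0.57 | 89.9% | 1.00 |
| 0.7 | 0.51 | 1.96 | 141 | 0.47 | 97.5% | 0.60 |

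ANCOVA costs one degree of freedom per covariate and otherwise does not lose to the unadjusted test. A raw change score improves on the unadjusted test only when r exceeds 0.5. The right response to the mismatch is therefore a covariate, not a subtraction.

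The detectable differences and powers assume the planned 36 per arm with a value for every man. The trial stopped short of that, so they illustrate scale only. Apart from degrees of freedom, the variance factors do not depend on the sample size.

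**4. Can CAPRA-S be expressed as a change?** No. Baseline CAPRA runs from 0 to 10 (section 4.1). CAPRA-S runs from 0 to 12 and counts surgical margin status and pathologic Gleason score (section 9.4.3), which come from the prostatectomy specimen. They are different instruments. Baseline CAPRA can serve as a covariate for CAPRA-S but cannot be subtracted from it.

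**The case against.** The strongest reply is that section 9.4.3 contains no error of inference. Under randomization the expected baseline is the same in both arms. The difference in mean post-surgery AQUA therefore has the same expectation as the difference in mean change, and the unadjusted, change-score and ANCOVA comparisons of means all target one effect. That stands. A reader might infer from the mismatch that the planned test is biased or answers a different question between the arms. It does not.

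Three further points also stand, in whole or in large part:

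- **CAPRA-S is not defined as a change.** The synopsis and section 9.1 name it as a post-surgical score, and the endpoint column of section 3 gives only the score. The comparison with baseline is in the justification column and in one procedural sentence of section 8.1. For CAPRA-S, section 9.4.3 is right to use the post-surgical score, and the other sections are loose.
- **No AQUA baseline is being thrown away.** The trial holds banked biopsy tissue, and section 8.1 has the assay run after enrollment closes. Assay of the biopsy rests mainly on the section 8.1 remark about men who miss surgery. The documents do not say that every biopsy will yield a value.
- **The SAP has overtaken much of this.** It makes secondary outcomes descriptive and lists neither endpoint, so a formal test may never be run.

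What the reply does not answer is why a baseline CAPRA score collected for randomization is left out, or why AQUA is handled differently from two assays planned on the same tissue. Nor does the SAP say how either endpoint would be presented if reported.

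**Conclusion.** The point holds as a matter of precision and consistency. Section 9.4.3 leaves out a baseline term that is collected anyway for CAPRA-S and that section 8.1 intends to measure for AQUA. It also leaves out the stratification factor. Sections 3, 8.1 and 9.1 need to be brought into line with it.

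The size of the loss is unknown, because it depends on r. Over an assumed range of 0.3 to 0.7, adjustment would cut residual variance by 9% to 49%. A reader might take the upper end, close to a doubling of effective sample size, as a demonstrated loss. The documents do not support that: they give no correlation for any AQUA marker or between CAPRA and CAPRA-S, and at r = 0.3 the gain is modest.

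Priority is low. These are secondary endpoints, the planned test is valid, and the SAP reports secondary outcomes descriptively.

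**What to change.** **In Protocol section 9.4.3:**

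- Compare post-surgery CAPRA-S between arms with baseline CAPRA score as a covariate. The stratum is a cut of that score.
- Compare post-surgery AQUA values by ANCOVA on the biopsy AQUA value, where the banked biopsy yields one, plus CAPRA stratum. State in advance how men without a biopsy value are kept in the comparison.
- Keep a rank-based version of each for use if normality fails. This matters most for CAPRA-S, a bounded score.

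**Elsewhere in the Protocol:**

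- In section 9.1, remove the before-and-after label for CAPRA-S only; for AQUA it fits section 8.1.
- In sections 3 and 8.1, remove the wording that sets CAPRA-S against baseline or the preoperative biopsy. The Gleason comparison in the same sentence of section 8.1 can stay.

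**In the SAP:** apply the same adjustment to any between-arm estimate of AQUA or CAPRA-S that is reported, and state that no difference from baseline is computed for CAPRA-S.

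**Cost:** for CAPRA-S, wording only, since the baseline score is already collected. For AQUA, wording plus the assay of banked biopsy tissue that section 8.1 already has in view, with the proviso that some biopsies may give no result.
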